Triple hit lymphoma
Trisomy 12
Tropical eosinophilia
Tropical sprue
Tuberculosis of intrathoracic lymph nodes
Tuberculosis of peripheral lymph nodes
Ultrasound spleen
Vaccination site lymphadenopathy
Vascular purpura
Venolymphatic malformation
Vitamin C deficiency
Von Willebrand's disease
Von Willebrand's factor activity abnormal

Von Willebrand's factor activity decreased
Von Willebrand's factor activity increased
Von Willebrand's factor activity normal
Von Willebrand's factor activity test
Von Willebrand's factor antibody
Von Willebrand's factor antibody positive
Von Willebrand's factor antigen abnormal
Von Willebrand's factor antigen decreased
Von Willebrand's factor antigen increased
Von Willebrand's factor antigen normal
Von Willebrand's factor antigen test
Von Willebrand's factor inhibition
Von Willebrand's factor multimers abnormal
Von Willebrand's factor multimers normal
Von Willebrand's factor multimers test
Waldenstrom's macroglobulinaemia
Waldenstrom's macroglobulinaemia recurrent
Waldenstrom's macroglobulinaemia refractory
Waldenstrom's macroglobulinaemia stage I
Waldenstrom's macroglobulinaemia stage II
Waldenstrom's macroglobulinaemia stage III
Waldenstrom's macroglobulinaemia stage IV
Warm type haemolytic anaemia
White blood cell agglutination present
White blood cell analysis
White blood cell analysis abnormal
White blood cell analysis normal
White blood cell count
White blood cell count abnormal
White blood cell count decreased
White blood cell count increased
White blood cell count normal
White blood cell disorder
White blood cell morphology
White blood cell morphology abnormal
White blood cell morphology normal
White clot in blood present
Wiskott-Aldrich syndrome
X-linked lymphoproliferative syndrome
Acquired C1 inhibitor deficiency
Acute generalised exanthematous pustulosis
Acute respiratory failure
Administration related reaction
Administration site dermatitis
Administration site eczema
Administration site hypersensitivity
Administration site photosensitivity reaction
Administration site rash
Administration site recall reaction
Administration site urticaria
Administration site vasculitis
Airway remodelling
Allergic bronchitis

HYPERSensitivity

Allergic colitis
Allergic cough
Allergic cystitis
Allergic eosinophilia
Allergic gastroenteritis
Allergic hepatitis
Allergic keratitis
Allergic oedema
Allergic otitis externa
Allergic otitis media
Allergic pharyngitis
Allergic reaction to excipient
Allergic respiratory disease
Allergic respiratory symptom
Allergic sinusitis
Allergic stomatitis
Allergic transfusion reaction
Allergy alert test positive
Allergy test positive
Allergy to chemicals
Allergy to fermented products
Allergy to immunoglobulin therapy
Allergy to surgical sutures
Allergy to vaccine
Alpha tumour necrosis factor increased
Alveolitis
Anal eczema
Anaphylactic reaction
Anaphylactic shock
Anaphylactic transfusion reaction
Anaphylactoid reaction
Anaphylactoid shock
Anaphylaxis treatment
Angioedema
Anti-insulin antibody increased
Anti-insulin antibody positive
Anti-insulin receptor antibody increased
Anti-insulin receptor antibody positive
Anti-neutrophil cytoplasmic antibody positive vasculitis
Antiallergic therapy
Antibody test abnormal
Antibody test positive
Antidiomysial antibody positive
Application site dermatitis
Application site eczema
Application site hypersensitivity
Application site photosensitivity reaction
Application site rash
Application site recall reaction
Application site urticaria
Application site vasculitis
Arthritis allergic
Aspirin-exacerbated respiratory disease

Asthma
Asthma late onset
Asthma-chronic obstructive pulmonary disease overlap syndrome
Asthmatic crisis
Atopic cough
Atopy
Auricular swelling
Blepharitis allergic
Blister
Blister rupture
Blood immunoglobulin A abnormal
Blood immunoglobulin A increased
Blood immunoglobulin D increased
Blood immunoglobulin E abnormal
Blood immunoglobulin E increased
Blood immunoglobulin G abnormal
Blood immunoglobulin G increased
Blood immunoglobulin M abnormal
Blood immunoglobulin M increased
Bromoderma
Bronchial hyperreactivity
Bronchial oedema
Bronchospasm
Bullous haemorrhagic dermatosis
Bullous impetigo
Caffeine allergy
Capillaritis
Catheter site dermatitis
Catheter site eczema
Catheter site hypersensitivity
Catheter site rash
Catheter site urticaria
Catheter site vasculitis
Charcot-Leyden crystals
Cheilitis
Childhood asthma
Choking
Choking sensation
Chronic eosinophilic rhinosinusitis
Chronic hyperplastic eosinophilic sinusitis
Circulatory collapse
Circumoral oedema
Circumoral swelling
Complement factor C1 decreased
Complement factor C2 decreased
Complement factor C3 decreased
Complement factor C4 decreased
Complement factor decreased
Conjunctival oedema
Conjunctivitis
Conjunctivitis allergic
Contact stomatitis
Contrast media allergy

Contrast media reaction
Corneal exfoliation
Corneal oedema
Cough variant asthma
Cross sensitivity reaction
Cutaneous vasculitis
Cytokine increased
Cytokine release syndrome
Cytokine storm
Dennie-Morgan fold
Dermatitis
Dermatitis acneiform
Dermatitis allergic
Dermatitis atopic
Dermatitis bullous
Dermatitis contact
Dermatitis exfoliative
Dermatitis exfoliative generalised
Dermatitis herpetiformis
Dermatitis infected
Dermatitis psoriasiform
Device allergy
Dialysis membrane reaction
Distributive shock
Documented hypersensitivity to administered product
Drug eruption
Drug hypersensitivity
Drug provocation test
Drug reaction with eosinophilia and systemic symptoms
Ear swelling
Eczema
Eczema infantile
Eczema nummular
Eczema vaccinatum
Eczema vesicular
Eczema weeping
Encephalitis allergic
Encephalopathy allergic
Eosinophil count abnormal
Eosinophil count increased
Eosinophil percentage abnormal
Eosinophil percentage increased
Eosinophilia
Eosinophilia myalgia syndrome
Eosinophilic bronchitis
Eosinophilic granulomatosis with polyangiitis
Eosinophilic oesophagitis
Eosinophilic pneumonia
Eosinophilic pneumonia acute
Eosinophilic pneumonia chronic
Epidermal necrosis
Epidermolysis
Epidermolysis bullosa

Epiglottic oedema
Erythema
Erythema multiforme
Erythema nodosum
Exfoliative rash
Eye allergy
Eye oedema
Eye swelling
Eyelid oedema
Face oedema
Fixed eruption
Flushing
Gastrointestinal oedema
Generalised bullous fixed drug eruption
Generalised oedema
Genital rash
Genital swelling
Giant papillary conjunctivitis
Gingival oedema
Gingival swelling
Gleich's syndrome
HLA marker study positive
Haemolytic transfusion reaction
Haemorrhagic urticaria
Hand dermatitis
Henoch-Schonlein purpura
Henoch-Schonlein purpura nephritis
Heparin-induced thrombocytopenia
Human anti-hamster antibody increased
Human anti-hamster antibody positive
Hypersensitivity
Hypersensitivity myocarditis
Hypersensitivity pneumonitis
Hypersensitivity vasculitis
Idiopathic urticaria
Immediate post-injection reaction
Immune complex level increased
Immune thrombocytopenia
Immune tolerance induction
Immunoglobulins abnormal
Immunoglobulins increased
Immunology test abnormal
Implant site dermatitis
Implant site hypersensitivity
Implant site photosensitivity
Implant site rash
Implant site urticaria
Incision site dermatitis
Incision site rash
Infusion related hypersensitivity reaction
Infusion related reaction
Infusion site dermatitis
Infusion site eczema

Infusion site hypersensitivity
Infusion site photosensitivity reaction
Infusion site rash
Infusion site recall reaction
Infusion site urticaria
Infusion site vasculitis
Injection related reaction
Injection site dermatitis
Injection site eczema
Injection site hypersensitivity
Injection site panniculitis
Injection site photosensitivity reaction
Injection site rash
Injection site recall reaction
Injection site urticaria
Injection site vasculitis
Instillation site hypersensitivity
Instillation site rash
Instillation site urticaria
Interstitial granulomatous dermatitis
Interstitial lung disease
Intestinal angioedema
Iodine allergy
Kounis syndrome
Laryngeal dyspnoea
Laryngeal obstruction
Laryngeal oedema
Laryngitis allergic
Laryngospasm
Laryngotracheal oedema
Leukotriene increased
Limbal swelling
Lip exfoliation
Lip oedema
Lip swelling
Localised oedema
Macrophage inflammatory protein-1 alpha increased
Mast cell activation syndrome
Mast cell degranulation present
Mechanical urticaria
Medical device site dermatitis
Medical device site eczema
Medical device site hypersensitivity
Medical device site photosensitivity reaction
Medical device site rash
Medical device site recall reaction
Medical device site urticaria
Mesenteric panniculitis
Monocyte chemotactic protein-2 increased
Mouth swelling
Mouth ulceration
Mucocutaneous rash
Mucocutaneous ulceration

Mucosa vesicle
Mucosal erosion
Mucosal exfoliation
Mucosal necrosis
Mucosal ulceration
Multiple allergies
Nasal crease
Necrotising panniculitis
Nephritis allergic
Neurodermatitis
Neutralising antibodies positive
Nikolsky's sign
Nodular rash
Non-neutralising antibodies positive
Noninfective conjunctivitis
Nutritional supplement allergy
Occupational asthma
Occupational dermatitis
Oculomucocutaneous syndrome
Oculorespiratory syndrome
Oedema mouth
Oedema mucosal
Oral allergy syndrome
Oral mucosal exfoliation
Orbital oedema
Oropharyngeal blistering
Oropharyngeal oedema
Oropharyngeal spasm
Oropharyngeal swelling
Palatal oedema
Palatal swelling
Palisaded neutrophilic granulomatous dermatitis
Palpable purpura
Panniculitis
Pathergy reaction
Penile exfoliation
Penile oedema
Penile rash
Penile swelling
Perineal rash
Perioral dermatitis
Periorbital oedema
Periorbital swelling
Perivascular dermatitis
Pharyngeal oedema
Pharyngeal swelling
Photosensitivity reaction
Pneumonitis
Procedural shock
Prurigo
Pruritus
Pruritus allergic
Pulmonary eosinophilia

Radioallergosorbent test positive
Rash
Rash erythematous
Rash follicular
Rash macular
Rash maculo-papular
Rash maculovesicular
Rash morbilliform
Rash neonatal
Rash papulosquamous
Rash pruritic
Rash pustular
Rash rubelliform
Rash scarlatiniform
Rash vesicular
Reaction to azo-dyes
Reaction to colouring
Reaction to excipient
Reaction to food additive
Reaction to preservatives
Reactive airways dysfunction syndrome
Red man syndrome
Respiratory arrest
Respiratory distress
Respiratory failure
Respiratory tract oedema
Reversible airways obstruction
Rhinitis allergic
Rhinitis perennial
SJS-TEN overlap
Scleral oedema
Scleritis allergic
Scrotal dermatitis
Scrotal exfoliation
Scrotal oedema
Scrotal swelling
Seasonal allergy
Septal panniculitis
Serum sickness
Serum sickness-like reaction
Shock
Shock symptom
Skin erosion
Skin exfoliation
Skin necrosis
Skin oedema
Skin reaction
Skin swelling
Skin test positive
Sneezing
Solar urticaria
Solvent sensitivity
Status asthmaticus

Stevens-Johnson syndrome
Stoma site hypersensitivity
Stoma site rash
Stomatitis
Streptokinase antibody increased
Stridor
Suffocation feeling
Sunscreen sensitivity
Swelling face
Swelling of eyelid
Swollen tongue
Symmetrical drug-related intertriginous and flexural exanthema
Throat tightness
Tongue exfoliation
Tongue oedema
Toxic epidermal necrolysis
Toxic skin eruption
Tracheal obstruction
Tracheal oedema
Tracheostomy
Transplantation associated food allergy
Type I hypersensitivity
Type II hypersensitivity
Type III immune complex mediated reaction
Type IV hypersensitivity reaction
Upper airway obstruction
Urticaria
Urticaria cholinergic
Urticaria chronic
Urticaria contact
Urticaria papular
Urticaria physical
Urticaria pigmentosa
Urticaria vesiculosa
Urticarial dermatitis
Urticarial vasculitis
Vaccination site dermatitis
Vaccination site eczema
Vaccination site exfoliation
Vaccination site hypersensitivity
Vaccination site photosensitivity reaction
Vaccination site rash
Vaccination site recall reaction
Vaccination site urticaria
Vaccination site vasculitis
Vaccination site vesicles
Vaccine associated enhanced disease
Vaccine associated enhanced respiratory disease
Vaginal oedema
Vaginal ulceration
Vasculitic rash
Vernal keratoconjunctivitis
Vessel puncture site rash

	Vessel puncture site vesicles
	Visceral oedema
	Vulval eczema
	Vulval oedema
	Vulval ulceration
	Vulvovaginal exfoliation
	Vulvovaginal rash
	Vulvovaginal swelling
	Vulvovaginal ulceration
	Vulvovaginitis allergic
	Wheezing
MANIC SWITCH	Hypomania
	Mania
	Manic symptom
NEUROLEPTIC MALIGNANT SYNDROME	Altered state of consciousness
	Autonomic nervous system imbalance
	Blood creatine phosphokinase MM increased
	Blood creatine phosphokinase abnormal
	Blood creatine phosphokinase increased
	Blood pressure abnormal
	Blood pressure decreased
	Blood pressure fluctuation
	Blood pressure increased
	Body temperature increased
	Cardiovascular insufficiency
	Catatonia
	Coma
	Confusional state
	Consciousness fluctuating
	Delirium
	Depressed level of consciousness
	Disorientation
	Dyskinesia
	Dyslalia
	Dysphagia
	Dystonia
	Dystonic tremor
	Extrapyramidal disorder
	Fatigue
	Freezing phenomenon
	Heart rate abnormal
	Heart rate increased
	Hyperhidrosis
	Hyperkinesia
	Hyperpyrexia
	Hypertension
	Hyperthermia malignant
	Hypertonia
	Hyporesponsive to stimuli
	Hypotension
	Labile blood pressure
	Labile hypertension
	Leukocytosis

	Loss of consciousness
	Malignant catatonia
	Muscle enzyme increased
	Muscle necrosis
	Muscle rigidity
	Muscular weakness
	Myalgia
	Myoclonus
	Myoglobin blood increased
	Myoglobin blood present
	Myoglobin urine present
	Myoglobinaemia
	Myoglobinuria
	Necrotising myositis
	Neuroleptic malignant syndrome
	Oculogyric crisis
	Opisthotonus
	Palpitations
	Parkinson's disease
	Parkinsonian crisis
	Parkinsonian rest tremor
	Parkinsonism
	Pyrexia
	Respiratory failure
	Resting tremor
	Rhabdomyolysis
	Salivary hypersecretion
	Serotonin syndrome
	Slow response to stimuli
	Stupor
	Tachycardia
	Tremor
	Unresponsive to stimuli
	Urinary retention
	White blood cell count abnormal
	White blood cell count increased
	Withdrawal catatonia
ORTHOSTATIC HYPOTENSION, DIZZINESS, AND SYNCOPE	Dizziness
	Dizziness postural
	Hypotension
	Orthostatic hypotension
	Presyncope
	Syncope
PROLACTIN	Amenorrhoea
	Amenorrhoea-galactorrhoea syndrome
	Anorgasmia
	Blood prolactin
	Blood prolactin abnormal
	Blood prolactin increased
	Breast discharge
	Breast enlargement
	Breast swelling
	Ejaculation disorder

	Erectile dysfunction
	Female orgasmic disorder
	Female sexual dysfunction
	Galactorrhoea
	Gynaecomastia
	Hirsutism
	Hyperprolactinaemia
	Hypomenorrhoea
	Lactation disorder
	Libido decreased
	Loss of libido
	Male sexual dysfunction
	Menstrual disorder
	Menstruation delayed
	Menstruation irregular
	Oligomenorrhoea
	Orgasm abnormal
	Orgasmic sensation decreased
	Prolactin-producing pituitary tumour
	Sexual dysfunction
QT PROLONGATION	Cardiac arrest
	Cardiac death
	Cardiac fibrillation
	Cardio-respiratory arrest
	Electrocardiogram QT interval abnormal
	Electrocardiogram QT prolonged
	Electrocardiogram U wave inversion
	Electrocardiogram U wave present
	Electrocardiogram U-wave abnormality
	Electrocardiogram repolarisation abnormality
	Long QT syndrome
	Long QT syndrome congenital
	Loss of consciousness
	Sudden cardiac death
	Sudden death
	Syncope
	Torsade de pointes
	Ventricular arrhythmia
	Ventricular fibrillation
	Ventricular flutter
	Ventricular tachyarrhythmia
	Ventricular tachycardia
RHABDOMYOLYSIS AND CPK ELEVATION	Acute kidney injury
	Anuria
	Biopsy muscle abnormal
	Blood calcium decreased
	Blood creatine phosphokinase MM increased
	Blood creatine phosphokinase abnormal
	Blood creatine phosphokinase increased
	Blood creatinine abnormal
	Blood creatinine increased
	Chromaturia
	Chronic kidney disease

Compartment syndrome
Creatinine renal clearance abnormal
Creatinine renal clearance decreased
Diaphragm muscle weakness
Electromyogram abnormal
End stage renal disease
Glomerular filtration rate abnormal
Glomerular filtration rate decreased
Haematoma muscle
Hypercreatininaemia
Hypocalcaemia
Muscle discomfort
Muscle disorder
Muscle enzyme increased
Muscle fatigue
Muscle haemorrhage
Muscle necrosis
Muscle rupture
Muscle strength abnormal
Muscular weakness
Musculoskeletal discomfort
Musculoskeletal disorder
Musculoskeletal pain
Musculoskeletal toxicity
Myalgia
Myalgia intercostal
Myoglobin blood increased
Myoglobin blood present
Myoglobin urine present
Myoglobinaemia
Myoglobinuria
Myopathy
Myopathy toxic
Myositis
Necrotising myositis
Oliguria
Renal failure
Renal impairment
Renal tubular necrosis
Rhabdomyolysis
Subacute kidney injury
Tendon discomfort
Thyrotoxic myopathy
1p36 deletion syndrome
2-Hydroxyglutaric aciduria
Acquired epileptic aphasia
Acute encephalitis with refractory, repetitive partial seizures
Alcoholic seizure
Alpers disease
Amygdalohippocampectomy
Aspartate-glutamate-transporter deficiency
Atonic seizures
Atypical benign partial epilepsy

Aura
Automatism epileptic
Autonomic seizure
Baltic myoclonic epilepsy
Benign familial neonatal convulsions
Benign rolandic epilepsy
Biotinidase deficiency
CDKL5 deficiency disorder
CEC syndrome
CSWS syndrome
Change in seizure presentation
Clonic convulsion
Congenital bilateral perisylvian syndrome
Convulsion in childhood
Convulsions local
Convulsive threshold lowered
Corpus callosotomy
Deja vu
Double cortex syndrome
Dreamy state
Drop attacks
Drug withdrawal convulsions
Early infantile epileptic encephalopathy with burst-suppression
Eclampsia
Epilepsy
Epilepsy surgery
Epilepsy with myoclonic-ataxic seizures
Epileptic aura
Epileptic psychosis
Faciobrachial dystonic seizure
Febrile convulsion
Febrile infection-related epilepsy syndrome
Foaming at mouth
Focal cortical resection
Focal dyscognitive seizures
Frontal lobe epilepsy
GM2 gangliosidosis
Gelastic seizure
Generalised onset non-motor seizure
Generalised tonic-clonic seizure
Glucose transporter type 1 deficiency syndrome
Grey matter heterotopia
Hemiconvulsion-hemiplegia-epilepsy syndrome
Hemimegalencephaly
Hyperglycaemic seizure
Hypocalcaemic seizure
Hypoglycaemic seizure
Hyponatraemic seizure
Idiopathic generalised epilepsy
Infantile spasms
Jeavons syndrome
Juvenile absence epilepsy
Juvenile myoclonic epilepsy

Lafora's myoclonic epilepsy
Lennox-Gastaut syndrome
Migraine-triggered seizure
Molybdenum cofactor deficiency
Multiple subpial transection
Myoclonic epilepsy
Myoclonic epilepsy and ragged-red fibres
Narcolepsy
Neonatal epileptic seizure
Neonatal seizure
Parietal lobe epilepsy
Partial seizures
Partial seizures with secondary generalisation
Petit mal epilepsy
Polymicrogyria
Post stroke epilepsy
Post stroke seizure
Post-traumatic epilepsy
Postictal headache
Postictal paralysis
Postictal psychosis
Postictal state
Preictal state
Schizencephaly
Seizure
Seizure anoxic
Seizure cluster
Seizure like phenomena
Seizure prophylaxis
Severe myoclonic epilepsy of infancy
Simple partial seizures
Status epilepticus
Sudden unexplained death in epilepsy
Temporal lobe epilepsy
Tongue biting
Tonic clonic movements
Tonic convulsion
Tonic posturing
Topectomy
Transient epileptic amnesia
Tuberous sclerosis complex
Uncinate fits
Fatigue
Hypersomnia
Malaise
Sedation
Sedation complication
Somnolence
Assisted suicide
Columbia suicide severity rating scale abnormal
Completed suicide
Depression suicidal
Intentional overdose

SOMNOLENCE

SUICIDALITY

Intentional self-harm
Poisoning deliberate
Self-injurious ideation
Suicidal behaviour
Suicidal ideation
Suicide attempt
Suicide threat
Suspected suicide
Suspected suicide attempt
Aseptic cavernous sinus thrombosis
Axillary vein thrombosis
Brachiocephalic vein occlusion
Brachiocephalic vein thrombosis
Budd-Chiari syndrome
Catheter management
Catheterisation venous
Cavernous sinus thrombosis
Central venous catheterisation
Cerebral venous sinus thrombosis
Cerebral venous thrombosis
Compression garment application
Deep vein thrombosis
Deep vein thrombosis postoperative
Embolism venous
Hepatic vein embolism
Hepatic vein occlusion
Hepatic vein thrombosis
Homans' sign positive
Iliac vein occlusion
Inferior vena cava syndrome
Inferior vena caval occlusion
Jugular vein embolism
Jugular vein occlusion
Jugular vein thrombosis
Mahler sign
May-Thurner syndrome
Mesenteric vein thrombosis
Mesenteric venous occlusion
Obstetrical pulmonary embolism
Obstructive shock
Ophthalmic vein thrombosis
Ovarian vein thrombosis
Paget-Schroetter syndrome
Pelvic venous thrombosis
Penile vein thrombosis
Peripheral vein occlusion
Peripheral vein thrombus extension
Phlebectomy
Portal vein cavernous transformation
Portal vein embolism
Portal vein occlusion
Portal vein thrombosis
Portosplenomesenteric venous thrombosis

Post procedural pulmonary embolism
Post thrombotic syndrome
Postoperative thrombosis
Postpartum venous thrombosis
Pulmonary embolism
Pulmonary infarction
Pulmonary microemboli
Pulmonary oil microembolism
Pulmonary thrombosis
Pulmonary vein occlusion
Pulmonary veno-occlusive disease
Pulmonary venous thrombosis
Renal vein embolism
Renal vein occlusion
Renal vein thrombosis
Retinal vein occlusion
Retinal vein thrombosis
SI QIII TIII pattern
Septic pulmonary embolism
Splenic vein occlusion
Splenic vein thrombosis
Subclavian vein occlusion
Subclavian vein thrombosis
Superior sagittal sinus thrombosis
Superior vena cava occlusion
Superior vena cava syndrome
Thrombophlebitis
Thrombophlebitis migrans
Thrombophlebitis neonatal
Thrombophlebitis superficial
Thrombosed varicose vein
Thrombosis corpora cavernosa
Transverse sinus thrombosis
Vascular graft
Vena cava embolism
Vena cava filter insertion
Vena cava filter removal
Vena cava thrombosis
Venogram abnormal
Venoocclusive disease
Venoocclusive liver disease
Venuous angioplasty
Venuous occlusion
Venuous operation
Venuous recanalisation
Venuous repair
Venuous stent insertion
Venuous thrombosis
Venuous thrombosis in pregnancy
Venuous thrombosis limb
Venuous thrombosis neonatal
Visceral venous thrombosis

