3.7.3.3 Vital Signs and Physical Examination

(1) Vital signs

(a) Time points

At screening, the initiation and Weeks 1, 4, and 8 (or discontinuation) of the antidepressant treatment period (Phase A), Weeks 1, 2, 3, 4, 5, and 6 (or discontinuation) of the double-blind period (Phase B), and Weeks 1, 2, 3, 4, 5, and 6 (or discontinuation) of the antidepressant-responder treatment-continuation period (Phase A+)

(b) Methods

After keeping the subject in a relaxed state, body temperature will be measured and then blood pressure (systolic and diastolic) and pulse rate will be measured in the supine, sitting, and standing positions in accordance with the measurement methods specified by the trial site. For body temperature, the date and result of measurement will be recorded in the source documents and the CRF. Blood pressure and pulse rate will be measured in the supine, sitting, and standing positions, in this order, after maintaining each position for at least 3 minutes. The date, time, positions, and results of measurement will be recorded in the source documents and the CRF.

(2) Physical examination

(a) Time points

At screening, the initiation and Weeks 1, 2, 3, 4, 6, and 8 (or discontinuation) of the antidepressant treatment period (Phase A), Weeks 1, 2, 3, 4, 5, and 6 (or discontinuation) of the double-blind period (Phase B), post-treatment observation period, and Weeks 1, 2, 3, 4, 5, and 6 (or discontinuation) of the antidepressant-responder treatment-continuation period (Phase A+)

(b) Methods

The investigator or subinvestigator will perform a physical examination that includes the assessment items shown below through subject interview and other relevant methods and record the physical findings in the source documents. The date and results of examinations at screening and only the dates of examinations after the initiation of the antidepressant treatment period (Phase A) will be recorded in the source documents and the CRF. Any clinically significant physical findings compared with findings at screening are to be recorded as AEs.

Assessment items: HEENT (head, eyes, ears, nose, and throat), chest, abdomen, urogenital organs, limbs, nerves, and skin mucosa

(3) Waist circumference

(a) Time points

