9.2.1 Adverse Events of Interest

Each adverse event of interest is defined in Appendix 4. Numbers and proportions of subjects with the following AEs of interest will be summarized by SOC and PT by treatment group and for the overall brexpiprazole group.

- Extrapyramidal AEs
- Neuroleptic malignant syndrome-related AEs
- Rhabdomyolysis
- Seizure-related AEs
- Orthostatic disorder-related AEs
- Suicide/suicide attempt-related AEs
- Oversedation-related AEs
- Hypersensitive symptom-related AEs
- Venous thrombosis
- Blood disorder-related AEs
- Glucose metabolism-related AEs
- Lipid metabolism-related AEs
- Body weight-related AEs
- QT interval prolongation-related AEs
- Manic switch-related AEs
- Prolactin increase-related AEs

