CT-8.7.2	Incidence of Drug-related TEAEs During Phase B of at Least 2% in Any Brexpiprazole Group and Greater Than Placebo by MedDRA System Organ Class and Preferred Term (Safety Analysis Set)
CT-8.8.1	Incidence of TEAEs During Phase B by MedDRA System Organ Class, Preferred Term and Time to First Onset (Safety Analysis Set)
CT-8.8.2	Incidence of Drug-related TEAEs During Phase B by MedDRA System Organ Class, Preferred Term and Time to First Onset (Safety Analysis Set)
CT-8.9.1	Incidence of TEAEs for EPS (Safety Analysis Set)
CT-8.9.2	Incidence of TEAEs During Phase B for Neuroleptic Malignant Syndrome (Safety Analysis Set)
CT-8.9.3	Incidence of TEAEs During Phase B for Rhabdomyolysis and CPK Elevation (Safety Analysis Set)
CT-8.9.4	Incidence of TEAEs During Phase B for Seizures (Safety Analysis Set)

CT-8.9.5	Incidence of TEAEs During Phase B for Orthostatic Hypotension, Dizziness, and Syncope (Safety Analysis Set)
CT-8.9.6	Incidence of TEAEs During Phase B for Suicidality (Safety Analysis Set)
CT-8.9.7	Incidence of TEAEs During Phase B for Somnolence (Safety Analysis Set)
CT-8.9.8	Incidence of TEAEs During Phase B for Hypersensitivity (Safety Analysis Set)
CT-8.9.9	Incidence of TEAEs During Phase B for VTE (Thrombotic and Embolic Events) (Safety Analysis Set)
CT-8.9.10	Incidence of TEAEs During Phase B for Haematopoietic/Leukopenia (Safety Analysis Set)
CT-8.9.11	Incidence of TEAEs During Phase B for Effect on Glucose (Safety Analysis Set)
CT-8.9.12	Incidence of TEAEs During Phase B for Effect on Lipids (Safety Analysis Set)
CT-8.9.13	Incidence of TEAEs During Phase B for Effect on Weight (Safety Analysis Set)
CT-8.9.14	Incidence of TEAEs During Phase B for QT Prolongation (Safety Analysis Set)
CT-8.9.15	Incidence of TEAEs During Phase B for Manic Switch (Safety Analysis Set)
CT-8.9.16	Incidence of TEAEs During Phase B for Effect on Prolactin (Safety Analysis Set)
CT-8.10.1	Incidence of TEAEs During Phase B by MedDRA System Organ Class and Preferred Term, by ADT (Safety Analysis Set)
CT-8.10.2	Incidence of TEAEs During Phase B by MedDRA System Organ Class and Preferred Term, by Gender (Safety Analysis Set)
CT-8.10.3	Incidence of TEAEs During Phase B by MedDRA System Organ Class and Preferred Term, by Age (Safety Analysis Set)
CT-8.10.4	Incidence of TEAEs During Phase B by MedDRA System Organ Class and Preferred Term, by CYP2D6 Metabolism Status (Safety Analysis Set)

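### The SAP's orthostatic hypotension, dizziness and syncope list counts Hypotension but not Blood pressure decreased, so CT-8.9.5 may under-count low-blood-pressure adverse events (minor)

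*SAP*

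**What the plan says.** SAP 9.2.1 names the categories of interest, among them "Orthostatic disorder-related AEs", and states: "Each adverse event of interest is defined in Appendix 4". Appendix 4 heads this category "ORTHOSTATIC HYPOTENSION, DIZZINESS, AND SYNCOPE" and gives it six preferred terms: *Dizziness*, *Dizziness postural*, *Hypotension*, *Orthostatic hypotension*, *Presyncope* and *Syncope*.

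The term "Blood pressure decreased" is in the Appendix 4 NMS list and in no other list. The NMS list also contains *Hypotension*.

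The table built from the orthostatic list is CT-8.9.5 in SAP Appendix 5, titled "Incidence of TEAEs During Phase B for Orthostatic Hypotension, Dizziness, and Syncope". The table built from the NMS list is CT-8.9.2.

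Protocol 3.7.3.3 schedules vital signs at each of Weeks 1 to 6 of Phase B and says: "Blood pressure and pulse rate will be measured in the supine, sitting, and standing positions, in this order".

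**The concern.** The category is not confined to postural events, since it takes in *Hypotension*, *Dizziness* and *Syncope* without qualification. A reader will take CT-8.9.5 as the grouped count of adverse events involving low blood pressure. Yet the same kind of event enters or misses the table according to whether the site's wording leads to a diagnosis term or a measurement term. Blood pressure is taken in three positions at every Phase B visit, so measurement wording is plausible for a low reading that the investigator judges to be an adverse event.

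At stake is the completeness of one grouped safety table. A low-blood-pressure event coded to the measurement term would appear, among the categories of interest, only under NMS, where few readers would look for it.

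**Working it through.** No sample-size, power or error-rate figure bears on this point. The check compares lists and traces where an event would be counted.

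**Step 1: is the list complete as published?** The six orthostatic terms run in alphabetical order from *Dizziness* to *Syncope*. They sit between the last NMS term (*Withdrawal catatonia*) and the prolactin list. Nothing suggests that terms were lost when the text was read from PDF.

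**Step 2: how do other Appendix 4 lists treat diagnosis and measurement terms?**

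| Appendix 4 list | Diagnosis term | Measurement term |
|---|---|---|
| Glucose | Hyperglycaemia | Blood glucose increased |
| Lipids | Hypercholesterolaemia | Blood cholesterol increased |
| Prolactin | Hyperprolactinaemia | Blood prolactin increased |
| NMS | Hypotension | Blood pressure decreased |
| Orthostatic | Hypotension | none |

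Of these five lists, only the orthostatic one has the diagnosis without the measurement.

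**Step 3: are the categories mutually exclusive?** They are not. *Hypotension* is in both the NMS and the orthostatic lists, and *Syncope* is in both the orthostatic and the QT lists. Placing *Blood pressure decreased* under NMS is therefore no reason to leave it out of the orthostatic list.

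**Step 4: where is a low-blood-pressure event in Phase B counted?**

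| Coded as | CT-8.2.1 (all TEAEs) | CT-8.9.2 (NMS) | CT-8.9.5 (orthostatic) |
|---|---|---|---|
| Hypotension | yes | yes | yes |
| Blood pressure decreased | yes | yes | no |

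**Step 5: how many could be missed?** In one arm, let *n* be the number of subjects with a low-blood-pressure TEAE. Let *p* be the share of them coded to *Blood pressure decreased* with none of the six listed terms reported as well. CT-8.9.5 then misses *p* × *n* subjects: none if *p* = 0, and all *n* if *p* = 1. A subject who also reports, say, dizziness is still in the table through that term. The documents give neither *n* nor *p*, so no narrower range can be supported.

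**Step 6: what else would show these events?** CT-11.2 applies the SAP Appendix 1 criteria:
- systolic pressure below 90 mmHg with a fall of at least 20 mmHg from baseline;
- diastolic pressure below 50 mmHg with a fall of at least 15 mmHg from baseline;
- for orthostatic hypotension, a systolic fall of at least 20 mmHg together with a pulse rise of at least 25 bpm from supine to sitting or standing.

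This cover is partial. An adverse event whose readings do not reach these thresholds is not flagged, and the table is built from readings, not from events that an investigator judged to be adverse.

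**The case against.** The strongest reply is that nothing here contradicts the SAP. Section 9.2.1 says that Appendix 4 defines the categories, and Appendix 4 does so. No rule for choosing terms is stated, and no text says that this term belongs. The NMS list gathers possible manifestations of a syndrome, so finding two terms together there does not make them synonyms. Protocol 5.2 asks for a single unifying diagnosis where possible, which works against measurement wording. Every TEAE is tabulated by preferred term in CT-8.2.1, *Blood pressure decreased* has its own row in CT-8.9.2, and low readings are reported separately.

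Most of this stands, and it limits the point to a possible under-count in one grouped table. It does not remove the point. The pairing also appears in the glucose, lipid and prolactin lists, which are not syndrome lists. Protocol 5.2 also allows individual signs when there is no unifying diagnosis.

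A reader might infer more than the documents support, in four ways:
- *That hypotension is understated in the brexpiprazole arms specifically.* The same list applies to placebo and reporting is blinded (Protocol 3.6). Any under-count could fall in any arm.
- *That the events are lost from safety reporting.* They are absent from CT-8.9.5 only.
- *That "Loss of consciousness" is also wrongly left out.* It is in the NMS and QT lists and not in this one, but it is not the measurement form of a listed term. Whether it belongs is a question of medical grouping that the documents do not settle.
- *That the SOMNOLENCE list, which includes terms such as "Sedation complication", is deficient without* Depressed level of consciousness *and* Stupor. Whether those terms mean oversedation is likewise a medical judgement.

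It may also be asked why *Labile blood pressure* or *Blood pressure fluctuation* should not be added on the same logic. Neither specifies a fall. *Blood pressure decreased* does, and it is the direct counterpart of a term already in the list.

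**Conclusion.** The gap is real but minor. As written, the plan leaves a low-blood-pressure TEAE out of CT-8.9.5 when it is coded to *Blood pressure decreased* and includes it when it is coded to *Hypotension*. The list comparison is a matter of record. The practical effect rests on the assumption that some such events will be coded to the measurement term, which is plausible but not shown. Its size cannot be stated without event rates. The primary analysis, the sample size and the overall adverse-event tables are untouched.

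The point is an improvement to one category list. It is not a contradiction in the SAP and does not bias the comparison towards any arm.

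**What to change.** Before unblinding, add *Blood pressure decreased* to the orthostatic hypotension, dizziness and syncope list in SAP Appendix 4, and generate CT-8.9.5 from the revised list. The term can stay in the NMS list, since the categories already overlap.

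The cost is one added term. The small downside is that an occasional fall in blood pressure that is not postural will be counted. Because SAP 9.2.1 has these tables presented by system organ class and preferred term, it will remain visible on its own row. If the narrow list is deliberate, a sentence in 9.2.1 giving the reason would let readers interpret CT-8.9.5 correctly.

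The sponsor's medical reviewers may wish to consider *Loss of consciousness* for this list, and *Depressed level of consciousness* and *Stupor* for SOMNOLENCE, at the same time. That is optional.
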